Non-adherence to the heart failure (HF) plan of care after hospital discharge has been associated with clinical outcomes, including the combined endpoint of all-cause mortality and rehospitalization for decompensated HF. Most patients are discharged with a complex set of instructions that include multiple medications (and differing medication administration plans), sodium restricted diet, fluid management actions (daily weight monitoring and in some cases, fluid restriction), monitoring signs and symptoms of HF, activity and exercise, and when to return for follow-up. At discharge, patients (and their families) may not understand that HF is chronic. Improvement in quality of life may be dependent on patients' acceptance of HF as a chronic, irreversible condition that requires self-care monitoring and behaviors (for example, becoming or staying physically active), even when they feel fine. To decrease the complexity of understanding HF, patients receive a HF handbook and a "zones" 1-page handout before discharge. In addition, they can watch multiple video clips of many HF topics and discuss HF self-care with the hospital healthcare team. However, patients may not read (or view) education materials due to health literacy issues, cognitive decline, eyesight issues, fatigue or depression. Patients may rely on lay (family) caregivers to understand self-care expectations and be active partners in care. Caregivers engaged in patients' care may not be present at discharge or may have preconceived or inaccurate ideas about HF self-care after discharge. A recorded message that could be repeatedly played by patients and caregivers might increase adherence to post-discharge self-care behaviors and 7-day follow-up appointments, and have clinical benefits related to a reduction in all-cause mortality and rehospitalization. The purposes of this randomized, controlled study are to examine the effects of use of a novel MyROAD (Recordable On-Demand Audio Discharge) card, given to patients at discharge. The aims of this single-blind, placebo-controlled study are to examine the effects of recorded messages that can be replayed post discharge (delivered via the MyROAD card) on (1) 45-, 90-, and 180-day *first occurrence* and (2) *time to first occurrence* of all-cause and HF-related hospitalization, ED visits and death/ cardiac transplantation/ventricular assist device, (3) 45-day quality of life, symptoms, functional status and perceived adherence to activity recommendations, and (4) 7-day follow-up appointment with the healthcare provider assigned before discharge. A total of 1066 patients (968 + 10% attrition) with decompensated HF will be randomized to either usual care or usual care and receiving a MyROAD card at discharge.

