Based on historical readmission rates among subjects receiving the current standard of care treatment (~ 20% and dropping slightly every year), a 30-day readmission rate of 18% is expected. We are also basing the sample size on an expected 90-day rehospitalization rate of 25% and a 180-day rehospitalization rate of 35%; both of which are conservative. Sample size calculations were performed to show minimum sample size needed to detect a decrease of 30% at 30-days, 90-days and 180-days with the addition of the card. In many research studies, trends toward improvement are found at 30 days, but the trend is not significant till further out (90 days or 180 days). Thus, we are hypothesizing that a trend will be seen at 30 days, but that there will be significant differences at 90 days and 6-months. A total sample size of 968, 734 and 468 are needed to achieve 80% power in 30-day, 90-day and 180-day rehospitalization rates, respectively. These calculations assumed a balanced randomization and use of one-sided Pearson chi-square tests with a significance level of 0.05. Calculations were performed using SAS software (version 9.2; Cary, NC). To account for attrition in follow-up, sample size was increased by 10-% at 30-days and 20% at 90- and 180-days, creating ideal sample sizes of 1066 (533 per group; to achieve power at 30-days), 882 (441 per group; to achieve power at 90-days) and 562 (281 per group; to achieve power at 180-days).

- Thus, our *minimum sample size* will be 562 subjects. If trends in outcomes are favorable, data collection will continue to reach the required sample size for 90-day outcomes.

Analyses

Patient characteristics will be summarized using frequencies and percentages for categorical factors, and means, standard deviations, and percentiles of interest for continuous measures. Pearson chi-square tests will be used to compare the proportion of subjects meeting the composite endpoint of death or at least 1 readmission by 6 months. Secondary analyses will use Poisson regression to compare readmission rates (number of readmissions/follow-up days), and competing risk survival methods will be used to compare time to first readmission between groups. Analyses will be performed assuming a 0.05 significance level. Analyses will be performed using SAS software (version 9.2 or higher; Cary, NC).

Feasibility

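### Attrition is allowed for by multiplying N by (1+d) rather than dividing by (1−d), so the 882 and 562 totals carry about 79% power, not 80%, if 20% is the expected loss

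*Combined protocol and SAP*

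**What the plan says.** The Sample Size section gives the numbers needed before attrition: "A total sample size of 968, 734 and 468 are needed to achieve 80% power in 30-day, 90-day and 180-day rehospitalization rates", using balanced allocation and a one-sided Pearson chi-square test at 0.05. The control rates are 18%, 25% and 35% at 30, 90 and 180 days, and the aim is to "detect a decrease of 30% at 30-days, 90-days and 180-days with the addition of the card".

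For attrition, "sample size was increased by 10-% at 30-days and 20% at 90- and 180-days". The resulting totals are 1066, 882 and 562, each labelled as the size that secures power at its time point. The minimum sample size "will be 562 subjects", and enrolment goes on towards the 90-day size if trends are favourable.

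The opening summary repeats the first total: "A total of 1066 patients (968 + 10% attrition". Sample and Setting also gives 1066 as the planned enrolment and says that it includes a 10% attrition rate.

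**The concern.** If a fraction d of enrolled patients is lost, the number enrolled must be N/(1−d) for N to remain. Multiplying by (1+d) leaves N(1+d)(1−d) = N(1−d²), which is always below N. The gap is 1% of N at d = 0.10 and 4% of N at d = 0.20, apart from rounding.

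This matters most for 882 and 562. The section allows enrolment to end at 562 and names 882 as the next target, so either could be the final size. It also hypothesises significant differences at 90 days and 6 months. At these two sizes there is no spare enrolment to absorb the gap.

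**Working it through.** **Inputs (Sample Size section).** Control rates p₁ of 18%, 25% and 35%; a 30% decrease read as relative, so p₂ = 0.7p₁ (the reading that fits the stated N); one-sided α = 0.05; 80% power; 1:1 allocation; d = 10%, 20%, 20%.

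**Step 1: reproduce the base N.** With p̄ = (p₁+p₂)/2, the number per arm is

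n = [1.645·√(2p̄(1−p̄)) + 0.842·√(p₁(1−p₁)+p₂(1−p₂))]² / (p₁−p₂)²

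- 90 days, 25% vs 17.5%: n = 366.8, so 367 per arm, **734**. Matches.
- 180 days, 35% vs 24.5%: n = 233.3, so 234 per arm, **468**. Matches.
- 30 days, 18% vs 12.6%: n = 548.5, so 549 per arm, **1098**. Does not match 968.
- 30 days, 20% vs 14%: n = 483.6, so 484 per arm, **968**. Matches.

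At 18%, a continuity correction (1170), a two-sided test (1394), both together (1468) and unpooled variance (1094) also fail to give 968.

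**Step 2: reproduce the inflated totals.** Per arm, rounded up:

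- 484 × 1.10 = 532.4 → 533, total **1066**
- 367 × 1.20 = 440.4 → 441, total **882**
- 234 × 1.20 = 280.8 → 281, total **562**

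All three match, so the method is N × (1+d). Dividing instead:

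- 484/0.90 = 537.8 → 538, total 1076
- 367/0.80 = 458.75 → 459, total 918
- 234/0.80 = 292.5 → 293, total 586

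**Step 3: evaluable patients if d is the loss rate.**

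| Time point | Enrolled | Evaluable | Needed | Short by |
|---|---|---|---|---|
| 30 days | 1066 | 1066 × 0.90 = 959.4 | 968 | 8.6 |
| 90 days | 882 | 882 × 0.80 = 705.6 | 734 | 28.4 |
| 180 days | 562 | 562 × 0.80 = 449.6 | 468 | 18.4 |

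**Step 4: power.** With n per arm,

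power = Φ{[√n·(p₁−p₂) − 1.645·√(2p̄(1−p̄))] / √(p₁(1−p₁)+p₂(1−p₂))}

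| Time point and control rate | Power at stated N | Power after loss | Cost of the method |
|---|---|---|---|
| 90 days, 25% | 80.0% (734) | 78.6% (705.6) | 1.4 points |
| 180 days, 35% | 80.1% (468) | 78.7% (449.6) | 1.4 points |
| 30 days, 20% | 80.0% (968) | 79.7% (959.4) | 0.3 point |
| 30 days, 18% | 75.5% (968) | 75.2% (959.4) | 0.3 point |

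**Step 5: full planned enrolment.** 1066 × 0.80 = 852.8 evaluable. Power is 85.0% at 90 days and 95.7% at 180 days.

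**Step 6: what a 20% increase covers.** 1 − 1/1.20 = 16.7%. At 90 and 180 days the totals keep 80% power for losses up to that level.

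**The case against.** Four points can be made for the plan.

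- **The 20% loss rate is inferred.** For 90 and 180 days the text gives only a 20% increase. Data Collection and Feasibility describe record review across the health system, telephone, mail and a possible death-index check, so loss for event outcomes could be below 16.7%. This stands: at these time points the shortfall is conditional. The increase is nevertheless said to be for attrition, and the same sentence handles the 10% in the same way, so 20% loss is the natural reading until a rate is given.
- **Planned enrolment is 1066.** At that size power is well above 80% at 90 and 180 days. This stands too: the gap at those time points arises only if enrolment stops at 882 or 562. The plan provides for such a stop.
- **The loss is smaller than the uncertainty in the inputs.** With 706 evaluable, a 90-day control rate of 26% gives 80.4%; with 450 evaluable, a 180-day rate of 36% gives 80.1%. The section itself calls its 90- and 180-day rates conservative. This limits the importance of the point but does not make the printed totals correct.
- **The 30-day figure has another cause.** A reader might take the roughly 75% power at 30 days as the result of the attrition method. It is not: power at 18% is already 75.5% with all 968 evaluable. The section says "a 30-day readmission rate of 18% is expected" after citing a historical rate of about "20% and dropping slightly every year", and 968 fits the historical rate.

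**Conclusion.** The attrition arithmetic is wrong as written if 10% and 20% are loss rates. Sample and Setting supports that for the 10%; for the 20% it is an assumption. On that basis the 882 and 562 totals give about 79% power at 90 and 180 days, and 1066 falls about 9 evaluable patients short of 968.

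A reader might infer that the trial is materially underpowered because of this. The documents do not support that: the method costs 0.3 to 1.4 points, and the full planned enrolment exceeds 80% at both later time points even with 20% loss. This is a small correction to stated figures. The mismatch between 968 and the stated 18% rate is larger, and it is a separate error.

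**What to change.** In Sample Size, state the loss rates expected at 30, 90 and 180 days. Keep 882 and 562 and restate their power after attrition as about 79%, or say that the 20% increase preserves 80% power only for losses up to 16.7%. This costs wording only.

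If 80% is to be kept in full, the N/(1−d) totals for the stated bases are 1076, 918 and 586: 10, 36 and 24 more patients.

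Separately, reconcile 968 with the 18% rate. Either state that the 30-day calculation used 20% vs 14%, or restate 30-day power at 18% as about 75%. Moving to 1076 would not repair this, since it leaves 968 evaluable and 75.5% power. At 18%, 80% power needs 1098 evaluable, or 1098/0.90 = 1220 enrolled. Then bring the opening summary and Sample and Setting into line with whatever is adopted.

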In brief, the research intervention is a novel card with 4 standardized, recorded messages of HF discharge instructions and a general message. (see Intervention section). The messages themselves are *not* the intervention, as the HF self-care messages are general standard of care messages delivered in many formats to hospitalized patients at all Cleveland Clinic hospitals. It is the ability to re-play (and re-listen) to general messages when desired that is the intervention.

Sample and Setting

A total of 1066 patients will be enrolled (533 per group) and consist of adults with chronic HF (diagnosis \geq 2 months) who are hospitalized for acute decompensated HF at the Cleveland Clinic main campus, Fairview Hospital, and Hillcrest Hospital. This sample size includes a 10% attrition rate.

Patients will have decompensated HF with preserved or reduced ejection fraction when hospitalized and New York Heart Association FC III or ambulatory IV. Diagnosis and etiology of HF will be confirmed in the electronic medical record prior to enrollment.

Inclusion Criteria:

1. Not referred for cardiac transplantation or ventricular assist device during the index hospitalization,
2. Minimum age 18 years (no upper age limit),
3. Ability to read and write,
4. Discharge to home or to a family member's home and has control of making self-care decisions,
5. Willing to participate; which requires three (3) follow-up telephone calls post-discharge.

Exclusions:

V1_01-20-16

NCT02901314

1. Chart documented psychiatric or cognitive conditions that limit ability to understand or adhere to self-care recommendations (Alzheimer's condition, dementia, schizophrenia, other neurological history that impairs memory),
2. Plans to discharge to assisted living apartment/center, skilled nursing facility or hospice care center,
3. Receiving home hospice or palliative care; or has a medical condition reflecting less than 1 year of survival (cachexia, end stage liver disease or cancer or non-ambulatory New York Heart Association functional class IV heart failure),
4. Post-cardiac transplantation or ventricular assist device placement,
5. Currently enrolled in another experimental HF research study,
7. Chronic renal failure and receiving chronic hemodialysis therapy for an estimated glomerular filtration rate $< 30 \text{ mL/minute/1.73 m}^2$,
8. A non-traditional form of HF (hypertrophic or restrictive forms of cardiomyopathy, congenital heart disease or Takotsubo cardiomyopathy).

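### Enrolment is fixed at 1066 in two places, but the Sample Size rule runs from 562 to 882 on an undefined favourable trend, and ending at 562 leaves 90-day power at 62-63%

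*Combined protocol and SAP*

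**What the plan says.** Three places in the combined protocol and SAP give the size of the trial.

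- **Opening summary:** "A total of 1066 patients (968 + 10% attrition) with decompensated HF will be randomized".
- **Methods, Sample and Setting:** "A total of 1066 patients will be enrolled (533 per group", stated to include 10% attrition. Neither statement is conditional.
- **Methods, Sample Size:** the three sizes are described as ideals, "creating ideal sample sizes of 1066 (533 per group; to achieve power at 30-days), 882 (441 per group; to achieve power at 90-days", followed by 562 for 180 days. The closing bullet then says that the minimum "will be 562 subjects. If trends in outcomes are favorable, data collection will continue to reach the required sample size for 90-day outcomes".

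The same section hypothesises only a trend at 30 days, but that "there will be significant differences at 90 days and 6-months". Sizing assumed "use of one-sided Pearson chi-square tests with a significance level of 0.05".

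The Analyses section names one chi-square comparison, to "compare the proportion of subjects meeting the composite endpoint of death or at least 1 readmission by 6 months". It adds "Analyses will be performed assuming a 0.05 significance level", without saying whether the tests are one-sided or two-sided. It mentions no interim look.

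**The concern.** The Sample Size bullet reads as the operative conclusion of its section, and it does not lead to 1066. Read literally, the largest size it reaches is 882, and that only if outcomes look promising. A reader cannot tell which of the three numbers is planned, nor what power the trial has for its 90-day comparison.

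The trigger is also open. Judging whether trends favour the card implies comparing the arms. The plan does not say on which outcome, at which time point, against what threshold, when or by whom. The extension is tied to 90-day outcomes, while the only chi-square endpoint named in Analyses is at 6 months. The plan also does not say whether a result at 562, the size presented as powered for 180 days, may be claimed. The planned size, the 90-day power and, on one possible reading, the type I error all depend on what is left unsaid.

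**Working it through.** **Inputs (Sample Size section).** Control readmission rates are 18%, 25% and 35% at 30, 90 and 180 days. The 30% decrease is read as relative, giving 12.6%, 17.5% and 24.5% with the card. One-sided 0.05, 80% power, 1:1 allocation. Attrition is 10% at 30 days and 20% at 90 and 180 days.

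**1. Reproduce the plan's sizes.** With p̄ the mean of the two rates, the Pearson chi-square size per arm is

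n = [1.645·√(2p̄(1−p̄)) + 0.842·√(p₁(1−p₁)+p₂(1−p₂))]² / (p₁−p₂)²

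- 90 days: (1.645×0.5785 + 0.842×0.5761)² / 0.075² ≈ 367 per arm, 734 in total. This matches.
- 180 days: (1.645×0.6465 + 0.842×0.6422)² / 0.105² ≈ 234 per arm, 468 in total. This matches.
- 30 days, 18% vs 12.6%: 549 per arm, 1098 in total. The plan states 968, which is exactly the size for 20% vs 14% (484 per arm).

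Attrition was applied by multiplication: 468×1.2 = 561.6, giving 562; 734×1.2 = 880.8, giving 882 as an even total; 968×1.1 = 1064.8, giving 1066 as an even total.

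**2. 90-day power if enrolment ends at 562.** Evaluable patients are 562/1.2 = 468 (the plan's convention) or 562×0.8 = 450 (20% actually lost), so about 234 or 225 per arm.

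Power = Φ([√n×0.075 − 1.645×0.5785] / 0.5761)

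- n = 234: Φ(0.340) = 63%
- n = 225: Φ(0.300) = 62%

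**3. Power at each candidate size** (same formula, both attrition conventions):

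| Enrolled | 90 days | 180 days |
|---|---|---|
| 562 | 62-63% | 79-80% |
| 882 | 79-80% | 92-93% |
| 1066 | 85-86% | 96% |

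At 1066, 30-day power for the stated 18% vs 12.6% is 75-76%, not 80%; at exactly 968 evaluable it is 75.5%.

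**4. Type I error, one-sided 0.05.** The threshold for a favourable trend is not given, so extension if z>0 or if z>1 at 562 is assumed. For one endpoint, the statistics at 562 and 882 have correlation √(562/882) = 0.798.

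- Only the final test counts: P(z₁ above the threshold and z₂>1.645) = 0.050 (z>0) or 0.042 (z>1).
- Claim possible at 562 and again at 882, same endpoint: two unrestricted looks give 0.075, so both cross with probability 0.05+0.05−0.075 = 0.025. The rule then gives 0.050+0.050−0.025 = 0.075 (z>0) or 0.050+0.042−0.025 = 0.067 (z>1).
- Claim possible on 180 days at 562 and on 90 days at 882: 0.081 (z>0) or 0.066 (z>1) by simulation. This assumes nested events at 35% and 25%: within-patient correlation √[(0.25×0.65)/(0.35×0.75)] = 0.787, and 0.787×0.798 = 0.628 between the statistics.

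These are scenario values, not a ceiling. They take enrolled numbers as information and assume that all 562 patients have complete follow-up at the look.

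**5. Sidedness.** If the final tests are two-sided at 0.05, 734 and 468 evaluable patients each give about 70% power rather than 80%.

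**The case against.** The strongest defence is that 562 is only a floor, that the text never says enrolment stops there, and that an extension on a promising trend acts like a futility rule. Much of this stands. Simulating the rule under the planned 90-day effect, with a claim only at the final test, enrolment ends at 562 in 3%, 7% or 16% of trials (extension if the 90-day z exceeds 0, 0.5 or 1). Average 90-day power is then 80%, 79% or 75%. The 62-63% figure applies only to a trial that actually ends at 562.

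Two stronger readings are tempting and are not supported.

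- A reader might infer that the rule inflates type I error. The plan describes no test at 562, and without a claim there the error stays near 0.05 or below. If stopping and extending led to tests of different endpoints, a final-test-only reading could give 0.0501-0.0507, a negligible excess.
- A reader might infer that low 30-day power at 562 or 882 contradicts the plan. It does not, because the Sample Size section expects only a trend at 30 days. The conflict with an expected significant result is at 90 days.

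A minimum with conditional extension is also legitimate once it is defined. What the defence does not answer is that two sections promise 1066 without condition, that the rule never reaches 1066, and that it makes continuation depend on outcomes rather than on recruitment or funding.

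**Conclusion.** The enrolment statements contradict each other and should be reconciled. The plan supports three different sizes, and the one set as the minimum gives 62-63% power at 90 days, where 80% was the design aim and significance is expected. This rests on the plan's own rates, a relative 30% reduction, one-sided 0.05 and its 20% attrition.

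On type I error the finding is an omission, not demonstrated inflation: about 0.04-0.05 if only the final test counts, and about 0.07-0.08 only under a claim at 562 followed by a second test at 882. The text leaves both open. Any reconciliation that keeps 1066 as the 30-day size must also deal with 968 not following from the stated 18% rate.

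**What to change.** 1. State one enrolment target in the opening summary, Sample and Setting, and Sample Size, and restate power at that size from the table above. If 1066 is kept as the 30-day size, report 30-day power as 75-76% for 18% vs 12.6%.
2. For the decision at 562, choose one:
   - delete the favourable-trend rule;
   - base the decision only on pooled event rate, recruitment and funding, with no comparison by arm;
   - state that the 562 data cannot support an efficacy claim if enrolment continues.
3. State whether the final test is one-sided or two-sided.

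A formal interim analysis should not be added unless its endpoint, the follow-up required at the look and any recruitment pause are specified. A 6-month endpoint needs 180 days after the 562nd patient's discharge, and recruitment may run on meanwhile.

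The cost is wording. Deleting the rule or pooling the data gives up the informal look by arm; barring a claim gives up an efficacy result at 562 when enrolment continues. None of these spends alpha. The reported power will be slightly less favourable. Naming 882 asks for no more patients than the current rule already allows; naming 1066 means 1066−882 = 184 more than that.

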physical limitations, symptoms, self-efficacy, social interference and quality of life.^{18, 19} KCCQ is valid, reliable and a responsive health measure.¹⁸ When 2 generic QOL tools were compared to KCCQ at baseline and 6 weeks for clinical changes, the KCCQ outperformed the 2 generic tools (EQ-5D and Rand 12).¹⁹ Ultimately, a mean change in score by 4.5 points (higher or lower) at 6 weeks reflected a change by 1 New York Heart Association functional class for overall summary score and a mean change in score by 5 points (higher or lower) at 6 weeks reflected a change by 1 New York Heart Association functional class for clinical summary score.¹⁹ Further, in previous research conducted at Cleveland Clinic in a study of patients with HF and similar enrollment criteria, the KCCQ was highly sensitive to changes in 60-day HF-related QOL between usual care and a 1-liter fluid restriction groups.²⁰

- Data will be collected at baseline and 45 days after discharge

Symptoms will be measured using a case report form that contains a list of commonly reported symptoms. Patients would place a check mark in the box of symptoms they have had in the last 7 days. This tool is essentially 1 item and should take about 30-60 seconds to complete. The tool has been used in previous research by the principal investigator and in analysis, patient perceptions of many signs and symptoms were highly associated with functional status and hospitalization.

- Data will be collected at baseline and 45 days after discharge

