Perceived adherence to activity/exercise recommendations will be measured using an investigator-developed form that is an extension of the physical activity and exercise case report form used in the 2009 exercise study conducted by the PI. The modified PACE tool is a 1-item tool with 17 response options that requires patients to select the option that reflects the highest level of purposeful walking, or moderate or vigorous exercise. The original PACE tool had 11 response options and focused only on moderate to vigorous exercise.

- Data will be collected at baseline and 45 days after discharge

Case report forms will be used to collect patient characteristics and medical history at baseline. The *Charlson Comorbidity Index* will be used to collect medical history. This index was developed to classify comorbid conditions which might change the risk of mortality.²⁵⁻³⁰ The score will be categorized into 3 groups (score of 1-2 = 1; 3-4 = 3; 5 or more = 5). In one study with 33,940 patients with ischemic heart disease, the grouping demonstrated a strong relationship with mortality rate.³⁰ This data will also be used to describe the sample groups for similarity in acuity.

- Data will be collected at baseline.

Data Collection

Medical records will be assessed for inclusion and exclusion criteria before approaching patients. Research personnel will explain the study in a patient's room (private in the J building and with the room-separating curtain closed when a double room on Main campus or at Hillcrest or Fairview Hospitals). After received verbal informed consent, patients will complete baseline data. After completing baseline paperwork, patients will be randomly assigned to the usual care or usual care plus MyROAD card group using block randomization; with blocks of 20 to decrease the influence of external factors that could alter outcomes. The randomization assignment will be made by a QHS statistician.

After randomization to groups:

- Intervention group patients will receive the MyROAD card by research personnel. The card can be administered at the time of enrollment, there is no need to wait till day of discharge, since voice-recorded messages are standard care and are not individualized. Patients will also be instructed that their healthcare providers (including their nurse caregivers) will deliver usual care discharge instructions and patient education.

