The main campus of Cleveland Clinic has a high volume of HF discharges each year. Fairview and Hillcrest Hospitals have moderate volumes of HF discharges, and are less likely to have patients who meet exclusion criteria due to enrollment in another research study or advanced HF. Electronic medical records allow for review of data on events that occur in *all* system hospitals and regional medical practice ambulatory care sites; decreasing the need to rely on patient recall of rehospitalization and emergency care events.

The MyCard instructions are a global representation of standard HF discharge instructions found in written handouts and other sources of patient education (videos, verbal instructions from healthcare providers). No new information is presented; thus, the MyRoad card is an extension of usual care delivered in a *different format that is repeatable*. Patients do not need to be able to

read and if they are forgetful, they can replay messages multiple times before the battery cycle ends (around 2 weeks of frequent use).

Nurse managers, clinical nursing directors and cardiologist medical directors of each hospital involved (7th floor J building and general medical units of main campus; multiple medical units of Hillcrest and Fairview Hospital—however, patients with HF are concentrated on PK2-Progressive Care Unit [Fairview Hospital] and 5M [Hillcrest Hospital] are aware that this study will be starting and agreed (and were actually excited) that we are included their patients/units. Research personnel from the Office of Nursing Research and Innovation will be involved in recruitment and all data collection. The main campus has multiple research projects in place. My team is accustomed to working with cardiology research nurses to ensure patients are not approached for more than 1 research study.

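### The main 6-month comparison is unadjusted, although Charlson group and symptoms are recorded at baseline and the plan links each to a component of the endpoint: a modest, cheaply recovered loss of efficiency

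*Combined protocol and SAP*

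**What the plan says.** - **Main comparison (Analyses).** "Pearson chi-square tests will be used to compare the proportion of subjects" with the composite of death or any readmission by 6 months. No covariate or stratum is named.
- **Secondary analyses (Analyses).** "Secondary analyses will use Poisson regression to compare readmission rates (number of readmissions/follow-up days), and competing risk survival methods will be used" for time to first readmission. No covariate is named here either.
- **Charlson index (Outcomes and Measurement).** It is collected at baseline and put into three groups. The plan reports that this grouping was strongly tied to mortality in a large cohort with ischemic heart disease. The planned use is given as: "This data will also be used to describe the sample groups for similarity in acuity".
- **Symptoms (Outcomes and Measurement).** A checklist is completed at baseline and at 45 days. Of earlier research with the same tool the plan says "patient perceptions of many signs and symptoms were highly associated with functional status and hospitalization".
- **Randomization (Data Collection).** Baseline forms are completed first. Allocation then uses "block randomization; with blocks of 20". Three hospitals enrol (Sample and Setting), and no stratification factor is stated.
- **Sample size.** The calculation rests on "use of one-sided Pearson chi-square tests with a significance level of 0.05". The control rate at 180 days is 35%, the effect a 30% relative reduction, and the stated minimum 562 patients.

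**The concern.** The endpoint has two components, death and readmission. The plan cites evidence that one baseline measure relates to death and another to hospitalization. Both are available for every patient before allocation, yet neither has a stated role in the treatment comparison.

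Two things are at stake. The first is precision: adjusting for a baseline variable that predicts the outcome narrows the interval for the treatment effect without recruiting anyone. The second is pre-specification. The plan will compare the groups on Charlson score but does not say what follows if they differ. An adjustment chosen at that stage would be post hoc and open to challenge.

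**Working it through.** **Inputs from the Sample Size section.** Control rate p1 = 0.35; intervention rate p2 = 0.35 × 0.70 = 0.245; one-sided alpha 0.05 (z = 1.645); power 80% (z = 0.842); 20% attrition; minimum N = 562. These are rehospitalization rates. The plan gives no rate for the composite, so they stand in for it here.

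**Step 1: reproduce the plan's figure.** With p̄ = 0.2975, √[2p̄(1−p̄)] = 0.6465 and √[p1(1−p1) + p2(1−p2)] = 0.6422:

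n per arm = [(1.645 × 0.6465 + 0.842 × 0.6422) / 0.105]² = 233.3, rounded up to 234, or 468 in total.

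This matches the stated 468, so the sample size and the unadjusted analysis agree with each other.

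**Step 2: power at the minimum after the planned loss.** 562 × 0.80 = 449.6, or 224.8 per arm.

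z = (0.105 × √224.8 − 1.645 × 0.6465) / 0.6422 = 0.795, which gives power of 78.7%.

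**Step 3: power with adjustment.** If baseline covariates explain a share R² of outcome variance, the effective size per arm is about 224.8 / (1 − R²). The documents give no R², so a range is shown.

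| R² (assumption) | Effective n per arm | Power |
|---|---|---|
| 0 (unadjusted) | 224.8 | 78.7% |
| 0.02 | 229.4 | 79.4% |
| 0.05 | 236.6 | 80.5% |
| 0.10 | 249.8 | 82.3% |

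Reaching 80% needs R² of about 1 − 224.8/233.3 = 0.036, or roughly 4%.

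**Step 4: check by simulation.** 3,000 trials were simulated per setting with N = 468, unstratified blocks of 20, three hospitals (60/20/20, assumed), a three-level Charlson group and one continuous baseline score. The adjusted test was the treatment term in a logistic model containing all three.

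| R² | Power, unadjusted | Power, adjusted |
|---|---|---|
| about 0.02 | 79.7% | 79.9% |
| about 0.06 | 80.5% | 82.2% |
| about 0.12 | 81.1% | 84.3% |

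With no treatment effect, the unadjusted test rejected in 4.6% to 5.4% of trials, against a nominal 5%.

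**Step 5: how much could chance imbalance by hospital matter?** Suppose one hospital supplies 30% of 562 patients (assumption) and one block sequence serves all sites. The arm-count difference within that hospital then has an SD of about √(562 × 0.3 × 0.7) = 10.9 patients. Relative to 281 per arm this is 10.9/281 = 3.9 percentage points. If that hospital's event rate differed from the others by 10 points (assumption), one SD of imbalance would move the risk difference by 0.039 × 10 = 0.4 points. The standard error of the risk difference is √[(0.2275 + 0.1850)/224.8] = 0.043, or 4.3 points.

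**The case against.** The strongest reply is that nothing is broken. An unadjusted chi-square after randomization is legitimate, its type I error is held, and the sample size was computed for exactly that test. All of this stands. A reader might infer that the planned comparison is biased or invalid; neither the documents nor the simulation supports that.

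The prognostic evidence is also thinner than it first looks. The Charlson statement concerns mortality in ischemic heart disease, not readmission in heart failure. The symptom statement gives no timing for when symptoms were measured. Both points stand, and they are why R² is left as a range that starts low.

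A reader might infer that the plan also treats hospital and the Kansas City questionnaire as prognostic. It does not. The questionnaire is described as valid, reliable and responsive, not as a predictor of events. The Feasibility remark that the two smaller-volume hospitals are "less likely to have patients who meet exclusion criteria due to enrollment in another research study or advanced HF" concerns patients who are screened out. It says nothing about differences among those enrolled. A reader might likewise infer that allocation is not stratified by hospital; the documents are only silent on this.

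Finally, the shortfall below 80% comes from inflating 468 by a factor of 1.2 rather than dividing by 0.8, which would give 585. That has its own direct remedy, and adjustment should not be credited with repairing it. The gain also matters less if recruitment continues. At the 1066 given elsewhere, with 20% loss (426.4 per arm), z = (0.105 × √426.4 − 1.063)/0.6422 = 1.72, and power is already about 95.7%.

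**Conclusion.** The point holds as a minor, optional improvement. The main comparison is unadjusted, no covariate is named for any analysis, and two baseline measures that the plan itself links to death or hospitalization have no stated analytic use. The cost is efficiency, not validity: at the 562 minimum with 20% loss, about 0.7 to 3.6 power points for R² between 0.02 and 0.10. The size rests on that assumed range, on the one-sided 0.05 level used for the sample size, and on the 35% rehospitalization rate standing in for the composite. It would be too strong to say that any small gain restores 80%, because an R² of 0.02 falls just short.

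Stratifying by hospital is a weaker matter. Under the assumptions in the working, the effect of chance imbalance is about a tenth of a standard error (0.4 against 4.3 points).

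**What to change.** 1. In Analyses, before any outcome data by group are seen, name the main estimate as the 6-month risk difference from a logistic regression with standardization, adjusted for Charlson group and baseline symptom count. Report the unadjusted chi-square alongside. A single named estimate is preferable to offering a Cox model as an alternative, since a hazard ratio answers a different question.
2. Add a simple rule for missing baseline symptom data.
3. State whether the block lists are separate by hospital. Preparing the blocks of 20 separately for the three hospitals and including hospital in the model is an optional low-cost addition.

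Cost: a few sentences of analysis text and, if step 3 is adopted, three lists instead of one. The adjusted result is slightly less simple to present than two proportions and a chi-square.
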